Our research center has used Redcap as the database for several previous and ongoing clinical studies. For this study, we will also use Redcap to setup and maintain a designated research database. The statistical packages will include both descriptive and quantitative data analyses using Sigma Stat (version 11) with the significance level at $P < 0.05$. [name] (20% effort), a statistician in our department, will be available for consultation. Descriptive analysis will be used to analyze the data obtained from various questionnaires (e.g., SF-MPQ-2; SF-36). Percent (%) changes in each category will be analyzed using the *Chi*-square test. Quantitative analysis will be used to analyze the data obtained from QST and VAS. **(A)** The Mann Whitney U test will be used to analyze the non-parametric data (e.g., results from the von Frey filament test). **(B)** For the parametric data, two-way repeated measure analysis of variance (ANOVA) will be used to examine differences across multiple groups at a given time point (between-group comparison) or across different test points for a given group (within-group comparison). The *post hoc* Waller-Duncan k-ratio t-test will be used to determine the source(s) of differences. Since ANOVA analyses do not take into consideration the fixed (e.g., drug dose) versus random (pain duration, age, etc.) effects on study outcomes, we will also use a simple mixed effects modeling (SPSS program) to analyze the interception among these factors. **(C)** Spearman Correlation Coefficient test will be used to examine correlations between clinical data (e.g., VAS change) and QST data. We will recruit equal numbers of male and female subjects so if there is sufficient statistical power for subgroup analysis, we will also analyze the sex/gender and ethnicity differences in our research data.

d. Power analysis

Estimation of group size (power analysis): Since VAS score change is a primary study outcome and previous studies have suggested that a VAS change of 2 points (or 30% from baseline) could be considered as clinically meaningful (Farrar et al., 2001; Cepeda et al., 2003; Grilo et al., 2007; Turk et al., 2008; Dworkin et al., 2009; Chen et al., 2009), we will use this parameter as the basis of power analysis. Thus, a group size of 37 subjects will have 80% power assuming that the standard deviation is less than 2 points (VAS). We anticipate a dropout rate of around 20%. Accordingly, we will recruit up to 45 subjects for each study group. If the dropout rate increases above 20%, we will add more subjects in each group to replace the dropouts beyond the estimated

20% rate. Since **a)** the MGH pain clinic alone receives over 15,000 visits per year, **b)** other pain clinics in the Boston area have a similar number of chronic pain patient visits (e.g., Brigham & Women's Hospital and Beth Israel Deaconess Medical Center), and **c)** we have established a referral network and have recruited about 500 subjects in our OIH studies, we are confident that we will be able to recruit the proposed number of subjects for this project.

VII. RISKS AND DISCOMFORTS

a. Complications of surgical and non-surgical procedures

1. Risks of QST

Common: Heat stimulation for pain threshold and tolerance tests, although transient may elicit pain. Heat stimulation may cause temporary skin sensitivity similar to mild sunburns. Immersion of a hand into a cool water (12 °C) bucket can be uncomfortable for subjects, particularly for those with pain in their upper extremities.

Uncommon: If a skin change persists, the subject will be withdrawn from the study and proper treatment will be given or the subject will be referred to a dermatologist.

2. Risks of blood drawing

Subjects may experience slight pain, discomfort, bleeding, bruising or, rarely, an infection from the blood draws. A total of 20 cc of blood will be drawn over the course of the study.

b. Drug side effects and toxicities

1. Morphine

Common side effects: decreased blood pressure, sleepiness, dizziness, drowsiness, dry mouth, upset stomach or throwing up, hard stools (constipation), headache, feeling tired or weak, abdominal pain, sweating, and pruritis.

Uncommon side effects: bronchospasm, change in pulse, hives, trouble breathing, loss of appetite, blurred or double vision, nervousness, sweating, and chills.

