The potential subject will be provided with information about the research through advertisements, Research Invitations, or reading a copy of the Consent Form. The potential subject can learn more about the study including potential benefits, risks, and discomforts by speaking with the study staff. The subject will be given as much time as needed to consider participating in the study. If the subject is eligible and decides to participate, he/she will be scheduled for a visit at the MGH Center for Translational Pain Research. At the first visit, the subject will read the Consent Form and then meet with a study physician via phone call to review and discuss the details of the study that are outlined in it. Any questions pertaining to the study will be answered at that time. If the subject agrees to participate, he/she will sign the Consent Form through a survey on REDCap with Adobe sign feature using a laptop provided or personal electronic device. The study physician will then log into REDCap right after and sign their signature. Two copies of the Consent Form will be printed with signatures from the REDCap website. The subject will take one copy and the other copy will be kept in his/her study folder. Subjects will have the option to meet with a study physician who is not their pain physician.

c. Treatment Assignment and Randomization

A total of 135 subjects will be enrolled for this double-blind, randomized study. Subjects will be randomized into three groups (n=45 subjects/group) using a computer-generated randomization protocol (Randomization.com).

- Group 1: morphine + placebo with acetazolamide
- Group 2: morphine + duloxetine with acetazolamide
- Group 3: placebo + duloxetine with acetazolamide

The duloxetine and placebo for duloxetine are specifically compounded with acetazolamide (15 mg), which will be used as a tracer to determine a subject's compliance with the study medication.

V. STUDY PROCEDURES

a. Study visits and parameters to be measured

Subjects will participate in a 10 week study consisting of three phases: Phase I is the dose titration period of 4 weeks, Phase II is the dose maintenance period of 4 weeks, and Phase III is the dose taper period of 2 weeks.

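### The sample-size figures do not agree: 45 per group at 20% dropout leaves 36, not 37, and 80% power at 37 does not follow from a 2-point difference with SD 2

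*Combined protocol and SAP*

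**What the plan says.** The power analysis (section VI.d) takes as its basis that "a VAS change of 2 points (or 30% from baseline) could be considered as clinically meaningful". With an SD assumed to be below 2 VAS points, it states that "a group size of 37 subjects will have 80% power". It continues "We anticipate a dropout rate of around 20" per cent and ends "Accordingly, we will recruit up to 45 subjects for each study group". If dropout goes above 20%, subjects are added to each group, but only to replace the dropouts in excess of that rate.

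Section IV.c repeats the result: "A total of 135 subjects will be enrolled for this double-blind, randomized study", in three groups of 45. The only significance level is in section VI.c: "with the significance level at $P < 0.05". Section VI.d does not name the test, its sidedness, the comparison that is powered (within a group, between two groups, or across three) or any adjustment for multiple comparisons. It does not say whether the SD is that of a single score or of a change.

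**The concern.** Section VI.d is the only justification for 135 subjects. A reader should be able to go from difference and SD to the evaluable number, and from there through dropout to the number recruited. Neither step works with the figures given. The second step also carries into the conduct of the trial, because the replacement rule is tied to the same 20%: at or above that rate it holds each group at 36, one below the number on which the paragraph rests. What is at stake is whether the stated power can be checked, and which evaluable number the trial is aiming for.

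**Working it through.** **Inputs.** From section VI.d: 37 per group, 80% power, 2 VAS points, SD below 2 (2 taken as the upper limit), dropout about 20%, 45 recruited per group. From section IV.c: 135 in total. From section VI.c: significance level 0.05. My assumptions: a two-sided two-sample t-test, with alternatives below.

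**Step 1: from 37 to 45.**
- Completers at 20% dropout: 45 x (1 - 0.20) = 36.
- Recruitment needed to keep 37: 37/(1 - 0.20) = 46.25, so 47 per group, or 3 x 47 = 141 in total against 135.
- The plan's 45 is reproduced by 37 x (1 + 0.20) = 44.4, rounded up. That multiplies by (1 + d) where division by (1 - d) is needed.
- Dropout at which 45 still leaves 37: 1 - 37/45 = 8/45 = 17.8%.
- Replacement: 9 of 45 is exactly 20%, so nobody is replaced and 36 remain. With 10 dropouts one is replaced, which restores 36 at best.

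**Step 2: from 2 points and SD 2 to 37.**
- Normal approximation: n = 2 x (1.960 + 0.842)^2 x SD^2/difference^2 = 2 x 7.85 x 4/4 = 15.7, so 16 per group. The exact t calculation gives 17.
- Power at n per group uses the noncentral t with noncentrality (difference/SD) x sqrt(n/2). For n = 36 this is 1 x sqrt(18) = 4.24 on 70 degrees of freedom, giving 98.7%. For n = 37 it is sqrt(18.5) = 4.30 on 72 degrees of freedom, giving 98.9%.

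Other readings of the paragraph, all for a 2-point difference:

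| Assumption | n per group for 80% | Power at 36 |
|---|---|---|
| Two-sided t, SD 2 | 17 | 98.7% |
| One-sided t, SD 2 | 14 | 99.5% |
| Bonferroni for three comparisons, SD 2 | 23 | 96.1% |
| Three-group ANOVA, means 0, 1, 2, SD 2 | 21 | 97.1% |
| Two-sided t, SD of change 2 x sqrt(2) = 2.83 | 33 | 84.1% |
| Bonferroni for three, SD of change 2.83 | 44 | 70.7% |

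The SD of 2.83 is that of a change between two uncorrelated scores, each with SD 2. A three-group ANOVA with that SD needs 40 (means 0, 1, 2) or 30 (means 0, 0, 2). A paired within-group test with SD 2 needs 10. None of these gives 37.

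**Step 3: what one subject is worth if 37 is taken at its word.** For 37 per group to give exactly 80% (two-sided t, 0.05), the standardised difference must be 0.660. That is 0.660 x 2 = 1.32 points at SD 2, or an SD of 2/0.660 = 3.03 for 2 points. With that standardised difference, 36 per group give 78.9%, a loss of 1.1 percentage points.

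**The case against.** The best defence is that the gap is trivial. Dropout is given as approximate, and 17.8% can fairly be called about 20%. One subject per group costs about one point of power even if 37 is exact. The plan also speaks of a group size of 37, not of 37 completers. Section VI.b compares VAS at weeks 0, 4, 8 and 10, and section VI.c adds mixed effects modelling, so a late dropout can still contribute data. No completer-only analysis set is defined. All of this stands, and it is why the point is minor. It does not make the figures agree: the plan inflates for dropout, so it treats dropouts as lost to the count, and at its own rate the count is 36.

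A reader might infer more than the documents support:
- **That the trial falls short of the 37 that 80% power requires.** On the stated difference and SD, 37 is not what 80% requires; 17 are enough under the assumed test. The 78.9% depends on a 1.32-point difference that was solved for and appears nowhere in the plan.
- **That 45 is a ceiling.** The sentence after the one that sets 45 allows more subjects once dropout passes 20%.
- **That correcting the text must lower the stated power.** At 2 points and SD 2 it raises it. Of the readings tabulated, power at 36 falls below 80% only when a larger SD of change and a Bonferroni adjustment are both added, and section VI.d states neither.
- **That enrolment is too large.** This does not follow either, because the comparison and the meaning of the SD are not stated.

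**Conclusion.** The paragraph is wrong as written in two places. The dropout step is pure arithmetic on the plan's own figures and needs no assumption beyond reading the rate as 20%: 36 remain per group, one short of 37, and the replacement rule does not restore it. The power step depends on an assumed test and sidedness, but under every variant tried the stated inputs fail to return 37 at 80%; with SD 2 the requirement for comparing groups is between 14 and 23 per group. The missing derivation of 37 is the larger of the two defects. Neither shows that the trial lacks its stated 80% power. Severity is minor: the text needs correcting and the design can stay.

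**What to change.** Keep 45 per group and 135 in total, and rewrite the power paragraph in section VI.d.

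1. State either that 45 per group with 20% dropout leaves 36 evaluable, or that 45 leaves 37 at a tolerated dropout of 17.8% (8 of 45). With the first, the replacement rule already fits. With the second, its threshold should move to the ninth dropout in a group.
2. Name the comparison, the test, its sidedness, any multiplicity adjustment, the difference, and the SD (of a score or of a change). Give the power that the chosen evaluable number provides under them. For example, 36 per group, a two-sided two-sample t-test at 0.05, 2 points and SD 2 give 98.7%.
3. If the sponsor had a smaller difference or a larger SD in mind when arriving at 37, say so and show the calculation.

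The cost is one rewritten paragraph. It needs no further subjects and no change to the randomisation or analysis. The restated power may come out well above or below 80%, depending on the assumptions the sponsor names.

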Group 1: Extended release morphine (15 mg) + placebo with acetazolamide (15 mg): Subjects will be titrated onto extended release morphine until their pain level is reduced to a VAS ≤ 3 or until the maximal tolerable dose (up to 60 mg/day) is reached. The placebo will be a sugar pill and will be compounded with acetazolamide (15 mg).

Group 2: Extended release morphine (15 mg) + duloxetine (30 mg) with acetazolamide (15 mg): Subjects will be titrated onto extended release morphine until pain level is reduced to a VAS ≤ 3 or until the maximal tolerable dose (up to 60 mg/day) is reached. Subjects will be titrated onto duloxetine until they have reached 60 mg/day. The duloxetine will be compounded with acetazolamide (15 mg).

Group 3: Placebo + duloxetine (30 mg) with acetazolamide (15 mg) The placebo will be a sugar pill. Subjects will be titrated onto duloxetine until they have reached 60 mg/day. The duloxetine will be compounded with acetazolamide (15 mg).

Morphine placebo and duloxetine placebo will have similar weight and packaging to the true morphine and true duloxetine in order to maintain blinding for subjects and study staff. The morphine/morphine placebo pills will be packaged in a different colored capsule than the duloxetine/duloxetine placebo so subjects can differentiate between the two pills. All medications will be taken orally, and will be prepared, dispensed, and coded by the MGH Research Pharmacy. The assignment will not be disclosed to the study subject or study staff.

Rescue medication:

Subjects in all three groups will be asked to stay on the same non-opioid pain medications, if any, without change once the study starts. Although no progression of overall pain condition is expected for study subjects, there may be sporadic breakthrough pain on top of an otherwise stable pain condition (i.e., no worsening of underlying pathology). This would be more likely to occur in the

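### Replacing dropouts beyond 20% restores numbers but not comparability: the rule does not say whether it works pooled or by arm, and no rule keeps subjects with incomplete follow-up in the VAS analysis.

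*Combined protocol and SAP*

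**What the plan says.** Section VI.d (Power analysis) holds that "a group size of 37 subjects will have 80% power", expects about 20% dropout and sets recruitment at up to 45 per group. If dropout goes higher, "we will add more subjects in each group to replace the dropouts beyond the estimated" 20%. It does not say whether the rate is counted overall or by arm, whether all three groups receive the same number of extra subjects, who does the counting, how the extra subjects are randomised, or where recruitment stops.

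Section IV.c fixes the total at 135: "Subjects will be randomized into three groups (n=45 subjects/group) using a computer-generated randomization protocol". Block sizes and list length are not described. On blinding, section V.b states: "The assignment will not be disclosed to the study subject or study staff". The same section has the research pharmacy prepare and code the drugs.

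Three other places bear on the point:

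- **IX.b (Safety monitoring):** a VAS score above 6 during the study leads to withdrawal, as do several side effects when profound.
- **VI.b (Study endpoints):** dropout is a secondary outcome, compared among the three groups with a Kaplan-Meier curve.
- **VI.c (Statistical methods):** VAS data go into a two-way repeated-measures ANOVA. A mixed-effects model is added to study factors such as dose, age and pain duration. No analysis set and no missing-data method is given.

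**The concern.** Two things are at stake.

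The first is operational. A rule that replaces dropouts within groups can be carried out in a way that needs arm-level information in a double-blind trial and sends late recruits to whichever arm lost most. The text neither requires this nor rules it out.

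The second matters more and does not depend on how the first is settled. Replacement treats dropout as a shortage of numbers. If subjects leave because of their pain score or their side effects, those who remain are a selected group, and the selection can differ between arms. New recruits pass through the same selection. The comparison of VAS among those who finish is then biased however many subjects are added, unless the analysis also uses the people who left.

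**Working it through.** **1. The plan's own figure.** The starting values are 37 evaluable per group and 20% dropout, both from VI.d. Multiplying gives 37 × 1.20 = 44.4, rounded up to the stated 45. Dividing, which is the correct inflation, gives 37 / 0.80 = 46.25, so 47. At exactly 20% dropout, 45 recruited leaves 45 × 0.80 = 36 completers, one short of 37 before the replacement rule starts.

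**2. What one round of replacement achieves.** The allowance is 45 × 0.20 = 9 dropouts per group. The rates above 20% are assumptions.

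| Dropout | Dropouts among 45 | Excess replaced | Enrolled | Completers |
|---|---|---|---|---|
| 30% | 13.5 | 4.5, so 5 | 50 | 50 × 0.70 = 35 |
| 40% | 18 | 9 | 54 | 54 × 0.60 = 32.4 |

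Replacements drop out too, so a single round does not bring back 37. The text does not say whether further rounds follow.

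**3. The two readings.** Suppose dropout is 40% in one arm and 20% in the other two. Arm-by-arm replacement adds 9 subjects to one arm (54, 45, 45) and needs that arm's count. A pooled trigger with equal additions needs only the overall rate and keeps the arms equal. At 30% overall, for example, 37 / 0.70 = 52.9, so 53 per arm and 159 in all.

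**4. Is dropout likely to be related to outcome and arm?** The protocol gives reasons to expect it.

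- Withdrawal above VAS 6 removes subjects on the primary outcome itself. Entry requires VAS of at least 6 (III.a), so many subjects can enter already above the withdrawal level. Sections III.a and IX.b need to be reconciled on this, but the present point does not depend on how.
- Constipation and dry mouth are grounds for discontinuation when profound (IX.b), and VII.b lists both as common with morphine and with duloxetine. One arm receives both drugs.
- V.b expects breakthrough pain to be more likely in the arm without extended-release morphine.

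**5. Illustration of the bias in a completer comparison.** Assume a normal VAS outcome with SD 2 (VI.d assumes an SD below 2), and that the worst-responding fraction p drops out. The mean of those who remain improves by 2 × φ(z_p) / (1 − p), where z_p is the p-quantile of the standard normal distribution and φ its density.

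- p = 0.20: 2 × 0.2800 / 0.80 = 0.70 points
- p = 0.30: 2 × 0.3477 / 0.70 = 0.99 points
- p = 0.40: 2 × 0.3863 / 0.60 = 1.29 points

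For arms with equal true means and dropout of 40% and 20%:

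| Dropout mechanism | Spurious difference |
|---|---|
| Random in both arms | 0 |
| Pain-driven in both arms | 1.29 − 0.70 = 0.59 |
| Pain-driven in the 40% arm, random in the 20% arm | 1.29 |

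In the two biased rows, the arm that loses more subjects looks better. The number recruited appears nowhere in the formula, so replacement leaves these values unchanged. VI.d says "a VAS change of 2 points (or 30% from baseline) could be considered as clinically meaningful", and 0.59 is 0.59 / 2, or about 30% of those 2 points.

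**6. Does the stated method keep those who left?** Repeated-measures ANOVA in its usual form uses only subjects with every time point. The mixed-effects model could use partial records, but VI.c does not give it that task or make it primary.

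**The case against.** A reader might infer that the rule unblinds staff, breaks the randomisation and removes dropouts from the analysis. The documents support none of these as fact.

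- **Group-by-group replacement.** The trigger is a single dropout rate following a single overall estimate. Adding subjects to each group fits equal additions to all three arms at least as well.
- **Unblinding.** Even arm by arm, the research pharmacy or the independent DSMB (IX) could hold the counts without telling study staff. The plan gives the task to nobody, which is a gap and not a breach.
- **Broken list or non-random allocation.** IV.c does not describe the list, and nothing says that added subjects would bypass randomisation. Unequal arm sizes alone do not bias a difference in means.
- **Dropouts excluded.** No sentence says so. The dropout comparison needs them, and the planned mixed model could keep their partial data.
- **The size.** The 0.59 points measures a completer comparison and not the replacement rule. Rewording the rule alone would not change it.

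All five stand, and they limit the claim. They do not remove the gap that is left. The plan sizes the trial on those who remain, speaks of replacing those who leave, names a main method that normally needs complete records, and withdraws subjects on the primary outcome. Nothing in it prevents a completer analysis. The missing analysis rule would matter even without replacement, but replacement is the only response to excess dropout that VI.d gives.

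**Conclusion.** The concern holds in a limited form. The replacement rule is open to two readings, and only one of them needs arm-level counts and directs subjects to arms. Under either, adding subjects does not restore comparability, and the analysis section has no rule that would.

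The figures are an illustration: 0.59 points when 40% and 20% dropout are both fully pain-driven, with 0 and 1.29 under the other two mechanisms shown. They rest on a normal outcome, SD 2, dropouts being exactly the worst responders where dropout is pain-driven, assumed dropout rates and an analysis of completers only. They do not bound the between-arm difference, since other mixtures of reasons for leaving give other values. The actual mechanism cannot be known from the documents.

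This should be corrected: the bias could reach a meaningful share of the 2-point change the plan treats as important, and the correction is cheap and right under either reading.

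**What to change.** 1. **VI.d:** reword the replacement sentence. If pooled dropout, counted without reference to treatment arm, exceeds 20%, total enrolment may rise to a stated maximum. All added subjects are randomised 1:1:1 by the same computer-generated procedure. Name who makes the count.
2. **VI.c:** state that all randomised subjects, including those who drop out, stay in the primary VAS comparison with all data collected. Make the already planned mixed-effects model, with group, visit and group-by-visit terms, the primary analysis. The VAS score that leads to a withdrawal should be among the data used.
3. **VI.c:** add a sensitivity analysis that varies the assumed outcomes of subjects after they leave, by arm.

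The cost is rewording in two sections and a small amount of extra analysis. The rewording itself requires no subjects beyond what VI.d already allows, which at present has no stated limit. The mixed model relies on data being missing at random. That may be doubtful for withdrawals due to side effects, and it is why the sensitivity analysis is needed.
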